Clinical Research Protocol

Title: Clinical study of CLDN 18.2-targeting chimeric antigen receptor-modified autologous T cells for CLDN 18.2-positive advanced solid tumors

Protocol No.: IMC002-CT01

Version: V2.0

Version date: 2022-01-25

Protocol synopsis

Title: Clinical study of CLDN 18.2-targeting chimeric antigen receptor-modified autologous T cells for CLDN 18.2-positive advanced solid tumors.
Protocol No.: IMC002-CT01
Version and date: Version 2.0; January 25, 2022
Type of study: IIT study (investigator-initiated trial)
Research Centers: 3
Investigational drug: chimeric antigen receptor-modified autologous T cells targeting CLDN 18.2 (hereinafter referred to as "CLDN 18.2 CAR-T" or "CAR-T" cells), codenamed IMC002 Dosage form and specification: Injection, $5 \times 10^7 \sim 3.5 \times 10^8$ CAR-T positive live cells
Mode of administration: Intravenous infusion
Indications: Advanced solid tumors with positive CLDN18.2 expression (including advanced gastric cancer/gastroesophageal junction cancer, advanced pancreatic cancer, and advanced ovarian cancer).
Number of cases: 10 to 30 cases
Research objectives Primary objective: 1) To observe and evaluate the safety and tolerability of advanced solid tumors patients with positive CLDN18.2 expression treated with intravenous infusion of IMC002. Secondary objectives: 1) To determine the maximum tolerated dose (MTD) and recommended phase II dose (RP2D) according to dose-limiting toxicity and clinical response including possible side effects after IMC002 treatment of advanced solid tumors patients with positive CLDN18.2 expression.

- 2) To evaluate the correlation of pharmacodynamic (PD) biomarkers with clinical efficacy to IMC002; the correlation of in vivo expansion and persistence of IMC002 and pharmacodynamic (PD) biomarkers and adverse events.
- 3) To evaluate the preliminary antitumor efficacy of IMC002 in patients with advanced solid tumors with positive CLDN18.2 expression using objective response rate (ORR), duration of response (DOR), disease control rate (DCR) and progression-free survival are used Phase (PFS) according to Response Evaluation Criteria in Solid Tumors (RECIST1.1), Immunotherapy Response Evaluation Criteria in Solid Tumors (iRECIST).
- 4) Incidence of treatment-related adverse events.

Exploratory Purpose:

- 1) To assess changes in immune status after IMC002 treatment.

Study design:

This study is a multicenter, single-arm, open-label, dose-escalation clinical study to evaluate the safety and preliminary anti-tumor efficacy of IMC002 treatment of CLDN18.2-positive advanced solid tumors.

This study plans to recruit 10 to 30 patients with advanced solid tumors with positive CLDN18.2 expression for autologous CAR-T cell therapy.

[figure not shown]

Figure 1. IMC002 Dose Escalation Design

Starting dose and dose escalation settings:

In this study, the accelerated titration and Bayesian optimal interval design (BOIN) is adopted, the starting dose is 1×10^6 cells/kg, and sequential doses are 3×10^6 , 5×10^6 , and 7×10^6 cells/kg, a total of 4 dose levels will be used.

1. Accelerated titration dose escalation:

The accelerated titration group is set as the first dose group, the dose is 1×10^6 cells/kg, and one subject will be enrolled and observed after administration, during the DLT observation period:

- If the subject has \geq grade 2 toxicity related to the study drug, the dose group will not be enrolled in other subjects and will be directly escalated to the next dose group.

2. Bayesian optimal interval design (BOIN) dose escalation

Step 1: Enroll 1-10 subjects in the low dose group (3×10^6 cells/kg), and then observe the number of subjects with DLT during the DLT observation period.

Step 2: Calculate the incidence of DLT, denoted by p , and compare it with the boundary values λ_e and λ_d given before the experiment. The dose level for the next cohort of subjects to be enrolled is determined.

The incidence of DLT (p) = the number of subjects with DLT at the current dose level / the total number of subjects enrolled at the current dose level.

λ_e and λ_d are calculated by the target toxicity probability DLT.

BOIN设计的剂量递增和递减边界

Boundary	Target toxicity rate for the MTD						
	0.1	0.15	0.2	0.25	0.3	0.35	0.4
λ_e	0.078	0.118	0.157	0.197	0.236	0.276	0.316
λ_d	0.119	0.179	0.238	0.298	0.358	0.419	0.479

The DLT rate in this study is set between 16% and 33%.

DLT率在30%的剂量递增表格

Action	The number of patients treated at the current dose																	
	1	2	3	4	5	6	7	8	9	10	11	12	13	14	15	16	17	18
Escalate if # of DLTs \leq	0	0	0	0	1	1	1	1	2	2	2	2	3	3	3	3	4	4
De-escalate if# of DLTs \geq	1	1	2	2	2	3	3	3	4	4	4	5	5	6	6	6	7	7

In the dose escalation phase, each dose group needs to complete the DLT observation before entering the next dose group; when the first subject in the same dose group has no DLT observed for at least 14 days after cell infusion, subsequent subjects can perform cell infusion.

If a subject withdraws from the study for reasons other than toxicity and does not complete the DLT observation period, the subject will be replaced to meet the requirements of the number of observation cases in each dose group.

The final dose should also consider the actual number of CAR-T cells produced and record the actual number of cells infused.

DLT observation time is 28 days after IMC002 infusion.

After the first CAR T cell infusion, if the investigator judges that the benefits of continued treatment outweigh the risks, based on the existing safety, CAR-T DNA copy number, and efficacy data, the investigator may consider continuing to give the subject IMC002 infusion more than one time (provided that there are enough qualified and quality CAR T cells to be used, and the infusion interval is 6-12 weeks), if appropriate, the next higher dose of IMC002 injection can be used.

For subjects who eligible for multiple infusion, if there are not enough qualified or quantity CAR T cells, the process of PBMC re-apheresis (if applicable), lymphodepletion, infusion procedures and safety visit procedures is the same with the first circle.

For patients who are judged by the investigator to be eligible for multiple infusions between 6-12 weeks, and ADA should be tested before IMC002 infusion.

Definition of Dosing Limiting Toxicity (DLT):

Adverse events (AEs) that occur during the study will be graded according to the National Cancer Institute (NCI) Common Toxicity Criteria (CTCAE 5.0), but a modified grading scale will be used to evaluate cytokine release syndrome as described in the protocol text.

The DLT for the dose escalation portion is defined as the following events possibly or definitely related to IMC002 that occurred within 28 days of infusion:

Hematological toxicity

- CLDN 18.2 CAR-T cell therapy-related hematological toxicity of grade ≥ 4 and cannot be recovered to grade ≤ 2 after 14 days of treatment (except for lymphocyte and leukopenia, non-febrile neutropenia).
- CLDN 18.2 CAR-T cell therapy-associated hemophagocytic lymphohistiocytosis (HLH)/hemophagocytic syndrome (HPS).

Non-hematological toxicity

- grade ≥ 4 non-hematological toxicity associated with CLDN 18.2 CAR-T cell therapy.
- CLDN 18.2 CAR-T cell therapy-related cytokine release syndrome \geq grade 3 cannot be controlled to grade ≤ 2 after 7 days of treatment.
- CLDN 18.2 CAR-T cell therapy-related grade 3 and above CAR-T cell therapy-related encephalopathy (CRES)/immune cell therapy-related neurotoxicity syndrome (ICANS).
- CLDN 18.2 CAR-T cell therapy-related grade 3 other non-hematologic toxicity persisting for more than 7 days, except:

- 1) \leq grade 3 fever or $>$ grade 3 fever recovered within 48 hours after adequate intervention to \leq grade 3;
- 2) \leq Grade 2 within 48 hours after adequate intervention;
- 3) Grade 3 fatigue;
- 4) Other laboratory abnormalities (such as alopecia) without significant clinical significance.

Definition of MTD:

BOIN design needs to be based on isotonic regression to estimate MTD after synthesizing subject information at each dose level. Statisticians can use the select.mtd of the R software BOIN package function to achieve, the specific procedure is as follows: select.mtd (target=0.3), npts =c (3,3,15,9,0), ntox =c (0,0,4,4,0)) / inside the numbers can be adjusted according to the actual situation.

Efficacy evaluation:

Efficacy evaluation will be based on RECIST 1.1 and iRECIST 1.1 for treatment response evaluation in solid tumors until 96 weeks after IMC002 infusion or disease progression, whichever occurs first.

Safety Assessment:

The study will collect all adverse events from the time the subjects sign the informed consent form until the subjects are discharged or other anti-tumor treatments are started, whichever occurs first. For subjects who have undergone leukapheresis but failed to reinfuse IMC002, only all adverse events reported within 30 days after the relevant operation or treatment (such as leukapheresis, pretreatment chemotherapy) or the initiation of a new antitumor therapy are collected, whichever occurs first.

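### Does the stated 16–33% DLT range leave the BOIN design without a usable target?

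*Protocol*

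**What the plan says.** The section of the protocol synopsis on BOIN dose escalation tells the team, in Step 2, to take the observed DLT proportion and "compare it with the boundary values λ_e and λ_d given before the experiment". It adds that "λ_e and λ_d are calculated by the target toxicity probability DLT". A table of λ_e and λ_d follows under the heading "Target toxicity rate for the MTD". It has seven columns, from 0.1 to 0.4, and none is marked as the one chosen. At 0.3 it gives 0.236 and 0.358.

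The next sentence is "The DLT rate in this study is set between 16% and 33" per cent. Directly after it comes the only table of escalation and de-escalation counts, for 1 to 18 patients. Its Chinese caption, "DLT率在30%的剂量递增表格", identifies it as the dose-escalation table for a DLT rate of 30%.

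Under Definition of MTD, isotonic regression is to be run with a call shown as "select.mtd (target=0.3), npts =c (3,3,15,9,0), ntox =c (0,0,4,4,0", followed by the remark that "inside the numbers can be adjusted according to the actual situation".

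**The concern.** Each BOIN target gives one pair of boundaries, so a range gives none. The only prose sentence about the study's DLT rate gives a range, and neither of its ends is a printed column. A reader could defend the 0.20, 0.25 or 0.30 column from that sentence. The remark about adjustable numbers does not say that the target is exempt.

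If the target really were open, escalation decisions and the selected dose could be argued either way once DLTs had been seen. MTD is part of the primary endpoint, and with 10 to 30 patients in the whole trial a single DLT in a small cohort often settles the next step.

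**Working it through.** **Inputs.** The λ table, the count table (36 cells: 18 escalation and 18 de-escalation limits) and the 16–33% range come from the BOIN section. The value 0.3 and the example counts come from Definition of MTD. The multipliers 0.6 and 1.4 are an assumption, as the protocol does not print them; the first step tests it.

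**Step 1: reproduce the plan's own figures.** With φ₁ = 0.6φ and φ₂ = 1.4φ:

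- λ_e = ln[(1−φ₁)/(1−φ)] / ln[φ(1−φ₁)/(φ₁(1−φ))]
- λ_d = ln[(1−φ)/(1−φ₂)] / ln[φ₂(1−φ)/(φ(1−φ₂))]

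At φ = 0.30, φ₁ = 0.18 and φ₂ = 0.42:

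- λ_e = ln(0.82/0.70) / ln(0.246/0.126) = 0.2365
- λ_d = ln(0.70/0.58) / ln(0.294/0.174) = 0.3585

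All seven printed columns agree to within 0.001. The printed 0.358 and 0.479 look truncated (0.3585 and 0.4797).

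Taking floor(n·λ_e) and ceil(n·λ_d) for n = 1 to 18 at φ = 0.30 gives all 36 printed counts. On a grid of 0.0001 from 0.16 to 0.33, only targets from 0.2989 to 0.3042 do so.

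**Step 2: what other targets in the range would do.**

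| Target | λ_e / λ_d | Cells changed, n = 1–18 (of 36) | Cells changed, n ≤ 10 (of 20) |
|---|---|---|---|
| 0.16 | 0.126 / 0.191 | 29 | 13 |
| 0.20 | 0.157 / 0.238 | 27 | 11 |
| 0.25 | 0.197 / 0.298 | 19 | 7 |
| 0.30 | 0.236 / 0.358 | 0 | 0 |
| 0.33 | 0.260 / 0.395 | 9 | 3 |

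The n ≤ 10 column matters because Step 1 of the BOIN section plans 1 to 10 subjects at 3×10^6 cells/kg; no cap is given for the higher doses.

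There are 65 possible outcomes with n ≤ 10 (the sum of n + 1 for n = 1 to 10). Compared with 0.30, the decision differs in 11 at a target of 0.20 and in 7 at 0.25, always by one step. For example, 1/3 and 2/6 de-escalate at 0.20 and 0.25 but stay at 0.30, and 1/5 stays at 0.20 and 0.25 but escalates at 0.30. Direct reversals were found only in comparisons involving a target at an end of the range: 1/5, 2/9 and 2/10 for 0.16 against 0.30, and 1/4 and 2/8 for 0.20 against 0.33.

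**Step 3: does the range generate any printed number?** Read as φ₁ = 0.16 and φ₂ = 0.33 around 0.30, it gives boundaries 0.225/0.315, not 0.236/0.358. Read as λ_e and λ_d themselves, 1/3 would de-escalate (the table says stay) and 1/5 would stay (the table says escalate). On neither reading does the range produce the printed rule.

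**Step 4: MTD selection.** With the protocol's example counts (unused fifth dose omitted) and estimates (y + 0.05)/(n + 0.1), the values are 0.016, 0.016, 4.05/15.1 = 0.268 and 4.05/9.1 = 0.445. They already increase with dose, so no pooling changes the choice. The third dose is closest to the target at 0.16, 0.20, 0.25, 0.30 and 0.33 alike.

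Other data can separate the targets. With assumed counts 0/1, 0/3, 1/6 and 2/6, the top two estimates are 1.05/6.1 = 0.172 and 2.05/6.1 = 0.336. Targets 0.20 and 0.25 then pick the third dose and 0.30 the fourth, although at 0.25 the distances are nearly equal (0.078 and 0.086).

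**The case for a change.** The best case for a change runs as follows. The BOIN target is a protocol matter and should not wait for an analysis plan. The one sentence that sets a rate sets a range. The table that resolves it is captioned in Chinese in a document otherwise in English. The adjustment remark does not protect the target. The cells that would change, such as 1/3 and 2/6, are ordinary results in small cohorts, and the repair would cost one line.

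Part of this stands. No sentence names 30% as the target or says what 16–33% means, and the selected MTD does depend on the target in principle, as the assumed counts show.

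The rest does not carry. The sentence speaks of a DLT rate, not of the target, and 30% lies inside its range, so it does not contradict the table. Every changed cell supposes that the printed table is discarded in favour of one the protocol does not contain. The adjustment remark follows a call filled with placeholder data: 15 patients at one dose, and five doses in a four-dose trial. Its natural meaning is that patient and DLT counts are replaced by those observed. Reading it as leave to move the target after seeing data is speculation.

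**Conclusion.** The range is a loose, unexplained sentence beside a rule that is fully specified and correctly calculated. The caption of the count table, the 0.3 boundary column and the MTD call all point to 0.30, and 36 of 36 counts agree with it. A site using the printed table has one action for each count. Defining or removing the range, and saying that the adjustable entries are the patient and DLT counts, would be tidier, but it would change none of those actions and no MTD selected under the rule as printed. No change to the plan is called for.

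This rests on two assumptions: that the standard multipliers apply, which the printed boundaries support, and that sites and statisticians follow the table and call they are given. It is a reading of what the protocol implements, not a view on which DLT rate is clinically acceptable.

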- 9) The production of IMC002 (CLDN 18.2 CAR-T cells) failed and a sufficient clinical dose of cells that met quality standards could not be obtained.
- 10) Safety reasons considered by the investigator.

Test Drug Dosage and Administration

Test drug: IMC002 (CLDN 18.2 chimeric antigen receptor T cell injection).

Codename: IMC002

Route of Administration: Intravenous infusion

Dosage:

Initial dose and dose escalation: this study adopted the dose escalation design of accelerated titration and Bayesian optimal interval design (BOIN). Four dose levels of 1×10^6 , 3×10^6 , 5×10^6 , and 7×10^6 cells/kg will be dose-escalated sequentially.

The final dose should also consider the actual number of CAR-T cells produced and record the actual number of cells infused.

Elimination criteria:

Before the statistical analysis of the data, the statistician and the principal investigator should discuss and judge whether the individual case is excluded. In the following cases, statisticians and investigators should comprehensively judge whether to exclude this subject based on factors such as the subject's degree of completion of the trial and the reasons for withdrawal, and not to be included in the set of compliance with the protocol, and make relevant explanations:

- 1) After participating in the trial, the subjects do not meet the inclusion criteria or meet the exclusion criteria or are judged to be major protocol deviations.
- 2) Not compliance with the protocol plan during the trial (poor compliance, such as IMC002 cells have not been used, or samples that cannot be evaluated for efficacy or safety according to the requirements of the trial protocol, without any data).

In addition to the above-mentioned cases, subjects who have other major deviations or violations of the protocol during the trial and have an impact on the efficacy and safety of IMC002 cells.

Criteria for early study termination:

Criteria for early termination of this study include but are not limited to the following:

1. Unexpected, significant, or unacceptable risk to enrolled subjects.
2. Enrollment is very slow and frequent protocol deviations.
3. Suspension or discontinuation of drug development.

Study endpoints and evaluation indicators

Primary endpoint: Safety and tolerability 28 days after a single infusion, to determine DLT and MTD.

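### The printed BOIN decision rule has no dose-elimination row, so a level with excess DLTs can be re-entered and nothing DLT-based ends dosing at the lowest level

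*Protocol*

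**What the plan says.** Under Study design in the Protocol synopsis, "the accelerated titration and Bayesian optimal interval design (BOIN) is adopted", with four dose levels. One subject is treated at the first level and BOIN starts at the second. In Step 2 the observed DLT rate at the current level is computed, and the instruction is to "compare it with the boundary values λ_e and λ_d given before the experiment"; from that comparison, "The dose level for the next cohort of subjects to be enrolled is determined".

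The count table is headed "DLT率在30%的剂量递增表格", that is, dose escalation at a 30% DLT rate. It has two action rows, "Escalate if # of DLTs" and "De-escalate if# of DLTs", for 1 to 18 subjects at the current dose. Staying at the level is implied between the two boundaries.

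Three other provisions bear on the point:
- The same section staggers infusions: later subjects in a dose group may be infused once the first has gone at least 14 days without a DLT.
- Definition of MTD applies isotonic regression once the data from all levels are combined.
- Criteria for early study termination lists "Unexpected, significant, or unacceptable risk to enrolled subjects", without a DLT count or probability and for the study as a whole.

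**The concern.** A rule that looks only at the current level and knows only up, stay and down keeps no record that a higher level has already failed. Once the level below looks acceptable, the same rule sends the next cohort back up. At the bottom of the range the de-escalate row has no level to point to, and no other rule tied to DLT counts applies.

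The primary endpoint is safety and the sample is 10 to 30 subjects. At stake are avoidable exposures at a level the trial's own data place above target, and subjects spent there rather than near the MTD. If investigators step in by judgement, the design that is run is no longer the one written.

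**Working it through.** **1. Reproduce the printed table.** With target φ = 0.30, φ₁ = 0.6φ = 0.18 and φ₂ = 1.4φ = 0.42:
- λ_e = ln(0.82/0.70) / ln[(0.30×0.82)/(0.18×0.70)] = 0.2365 (printed 0.236).
- λ_d = ln(0.70/0.58) / ln[(0.42×0.70)/(0.30×0.58)] = 0.3585 (printed 0.358).

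The rows floor(nλ_e) and ceil(nλ_d) match the printed table at all 18 sample sizes. The table is arithmetically right for 0.30.

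**2. Evidence after a bad cohort.** With a uniform prior, the posterior after y DLTs in n subjects is Beta(1+y, 1+n−y).
- 3/3: Pr(rate > 0.30) = 1 − 0.3⁴ = 1 − 0.0081 = 0.992.
- 4/6: 0.971.

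**3. A path through the table.** Suppose 3×10⁶ shows 0/3, so the trial escalates, and 5×10⁶ then shows 3/3. The table says de-escalate. Counts at 3×10⁶ are cumulative and the escalate boundary at n = 6 is 1, so 0 or 1 DLT in the next three subjects sends the trial back to 5×10⁶.
- True rate 0.10 at the lower level: the chance of 0/3 is 0.9³ = 0.729; of at most 1/3, 0.729 + 3×0.1×0.81 = 0.972.
- True rate 0.15: 0.85³ = 0.614; and 0.614 + 3×0.15×0.7225 = 0.939.

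**4. How often, and at what cost.** The simulation inputs below are assumptions unless stated in the Protocol: at most 30 subjects (Protocol), one titration subject (Protocol), cohorts of 3, a level counted as past the limit when Pr(rate > 0.30) > 0.95 with n ≥ 3, de-escalation from 3×10⁶ to 1×10⁶ allowed, and dosing continued at 1×10⁶ when de-escalation is indicated there. Runs were made with and without a cap of 10 per level, and with and without the 14-day stagger, modelled as ending a cohort when its first subject has a DLT.

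| True DLT rates, % | Setting | Trials with subjects treated at or above a level past the limit |
|---|---|---|
| 5/15/50/70 and 10/50/60/70 | cap 10, no stagger | 51–53% |
| same | cap 10, stagger | 23–33% |
| same | no cap, with or without stagger | 46–64% |
| 5/10/20/30 | all settings | 6–11% |

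Repeat runs differ by a few percentage points; for example, the first row came out at 47–51% in another run. A still steeper curve, 2/5/60/80 with no cap or stagger, gives 83% with cohorts of 3.

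Subjects at levels with true DLT rate of at least 40%, without and with elimination:
- 5/15/50/70, cap 10, no stagger: 9.7 against 7.9.
- 5/15/50/70, no cap, no stagger: 14.2 against 10.7.
- 10/50/60/70, no cap, no stagger: 17.3 against 12.8.

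Across all settings for the two steep curves the saving is about 0.8–4.7 subjects and 0.3–1.9 DLTs per trial. In the mildest setting (5/15/50/70, cap and stagger) one run gave 6.8 against 6.2, a saving of 0.6. In the capped runs part of the saving is lower enrolment: a mean of 20.2 subjects against 18.4 for 5/15/50/70 without stagger.

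**5. All levels toxic (50/60/70/80), no cap.** The printed table doses all 30 subjects, with about 15–16 DLTs. With elimination it is about 15–18 subjects and 8–10 DLTs.

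**The case against.** - *A rule may exist elsewhere.* Figure 1, which shows the escalation design, is not available, and an SAP may hold operating detail. This lowers confidence. It does not remove the point, because the Protocol itself prints the table that assigns doses and its text refers to no closure rule.
- *The table is correct.* It is, for a 30% target. A reader might infer that the boundaries are wrong, and they are not. The fault is a missing action.
- *Cumulative counts push the trial back down.* Usually after one cohort. That cohort is the avoidable exposure, and nothing prevents a second return.
- *The 14-day stagger already protects subjects.* It helps a good deal: with a cap of 10, the re-entry rate roughly halves. A run of 3/3 in one cohort would need dosing to continue after the first subject's DLT, or that DLT to appear after day 14. The model is also generous to the stagger, since it treats every cohort as staggered and every DLT as seen by day 14. Without a cap, re-entry with the stagger is still 46% or more in the steep scenarios.
- *The investigators can stop the study.* True, so it would be wrong to infer that the trial has no safety stop. The criterion is qualitative and study-level, and it does not close a dose level.
- *The scenarios are chosen to be steep.* Fair. Under the gentle curve the rate is only 6–11%.

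**Conclusion.** The point stands as an omitted safeguard in a decision rule that the Protocol itself fixes. Re-entry is possible, not certain. A reader might infer that about half of such trials would re-expose subjects, but the documents do not support a single figure. They fix neither the cohort size nor a per-level cap (1–10 subjects is stated only for 3×10⁶), and they give no posterior limit or prior. The supportable statement is a range: about 23–64% under the two steep curves and 6–11% under the gentle one. The typical gain is moderate, often about one DLT per trial. It is large only if every level is toxic, and that result assumes that dosing continues at the lowest level, where the text is silent. The change should be made; confidence is medium, mainly because Figure 1 is not shown.

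**What to change.** Add a third row to the decision table giving the DLT count at which the current and higher levels are eliminated. Compute it from the same 0.30 target, at a posterior cutoff and prior that the sponsor pre-specifies. State what the row means at the lowest level, and have the MTD selection exclude closed levels. The text also gives a DLT range of 16% to 33%; the new row needs the single target that the table uses.

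As illustration only, a 0.95 cutoff with a uniform prior gives 3, 3, 4, 4, 5, 5, 5, 6 DLTs at n = 3 to 10; a 0.90 cutoff gives 2 at n = 3.

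The cost is one table row and a short paragraph in an amendment, with no extra subjects. The downside is that an acceptable level is sometimes closed by chance. For a true rate of 0.25, closure at n = 3 alone has probability 0.25³ = 0.016 at the 0.95 cutoff, but 3×0.25²×0.75 + 0.25³ = 0.156 at 0.90; later looks add to both. The sponsor should quantify this over the whole trial when choosing the cutoff.

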Before lymphodepletion and 3 days before IMC 002 infusion, if the investigator judges that the subject has significant abnormalities; or the investigator judges that the subject has rapid disease progression compare to the screening time; or the investigator assesses that the patient has significant organ dysfunction (such as severe heart disease, uncontrollable hypertension or diabetes, severe liver or kidney damage, pulmonary edema, severe lung infection, brain metastasis); and it is not suitable for follow-up test procedures, then the lymphodepletion cannot be continued or should be delayed; the CAR T cells should not be infused or the infusion should be delayed.

If the infusion of cells is delayed for more than 5 days after lymphodepletion for any reason, the infusion is not allowed or needs to be delayed.

Withdrawal criteria:

- Subjects may withdraw from the study at any time of their choice.
- Subjects who did not complete the study protocol, including cell infusion and follow-up assessments, are considered to have terminated the study early.
- The reason for termination must be recorded in the CRF and maintained for the specified period of time as required by GCP.
- Subjects may be withdrawn from the study at any time during the study at the discretion of the investigator for reasons of subject safety, behavior, or management reasons, including:
 - 1) Disease progression confirmed by imaging and iRECIST criteria.

- 2) The cumulative treatment reached 96 weeks (no radiographic progression).
- 3) The subjects experienced serious adverse reactions.
- 4) Subject died.
- 5) Subject is pregnant.
- 6) Major protocol deviation included, but not limited to:
 - a) Mistaken for failing to meet inclusion/exclusion criteria
 - b) Concomitant use of prohibited drugs in this protocol
 - c) The subjects did not cooperate with the treatment and follow-up, are lost to the follow-up, or the subjects did not come to the hospital for more than two follow-up visits on time.
- 7) The disease progressed rapidly before the cell infusion, and the investigators determined that other treatment regimens needed to be used based on the maximum benefit of the subjects.
- 8) In the absence of efficacy, the investigator determined that the subject did not benefit from the trial treatment, and continued participation in the study may put the patient at unacceptable risk.

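### A dose group may go on being infused after its DLT count already makes de-escalation certain; one closure sentence would prevent this

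*Protocol*

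**What the plan says.** All references are to the Protocol synopsis, mainly Starting dose and dose escalation settings.

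- **BOIN, Step 1.** One to ten subjects are enrolled at 3×10^6 cells/kg, "and then observe the number of subjects with DLT during the DLT observation period".
- **BOIN, Step 2.** The observed DLT rate is compared with the boundaries: "The dose level for the next cohort of subjects to be enrolled is determined".
- **Escalation table (30% target).** The de-escalate counts for 1 to 10 treated are 1, 1, 2, 2, 2, 3, 3, 3, 4, 4.
- **Within a group.** Only the first subject is gated: when "the first subject in the same dose group has no DLT observed for at least 14 days after cell infusion, subsequent subjects can" be infused. The DLT window is 28 days.
- **Between groups.** "each dose group needs to complete the DLT observation before entering the next dose group".
- **Replacement.** For a subject who leaves early for reasons other than toxicity, "the subject will be replaced to meet the requirements of the number of observation cases in each dose group".

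The text gives no group size for 5×10^6 or 7×10^6. Figure 1, the escalation scheme, is not reproduced in the copy reviewed and may give one.

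**The concern.** Step 1 reads as fill the group, then count. Step 2 acts on the next cohort. The replacement rule also suggests that groups are filled to a set number. After the first-subject gate opens, halfway through that subject's DLT window, no DLT in subjects 2, 3, 4 and so on has a stated consequence for those still waiting in the same group.

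The other safeguards do not use a DLT count. The re-evaluation before lymphodepletion and infusion looks at the individual subject's condition. The withdrawal and early-termination criteria are matters of judgement.

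A planned group of 10 with 4 DLTs in its first 7 subjects will de-escalate whatever happens next, because the printed number for 10 is 4. Yet nothing written stops the remaining 3 infusions at that dose. In a CAR-T escalation whose primary objective is safety, those infusions expose subjects without any prospect of changing the group's decision.

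**Working it through.** **1. The printed table is right.** With the usual BOIN settings at target φ = 0.30, φ1 = 0.6φ = 0.18 and φ2 = 1.4φ = 0.42:

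- λ_e = ln(0.82/0.70) / ln[(0.30×0.82)/(0.18×0.70)] = 0.2365 (printed 0.236)
- λ_d = ln(0.70/0.58) / ln[(0.42×0.70)/(0.30×0.58)] = 0.3585 (printed 0.358)

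Rounding n×λ_d up gives 2 at n = 3, 3 at n = 6 and 4 at n = 10, as printed. All 18 columns match. The issue is when the table is applied, not its contents.

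**2. When is de-escalation certain?** Let N be the planned group size and d the printed de-escalate count at N. A DLT count cannot fall, so once it reaches d the group must de-escalate when full. Closing at that moment can never be a false closure.

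**3. Avoidable infusions.** Assumptions: first group at the level, subject 1 DLT-free, independent DLTs with true rate p, each outcome known before the next infusion. Among the M = N − 1 later subjects, the d-th DLT falls on the j-th with probability C(j−1, d−1) p^d (1−p)^(j−d), leaving M − j infusions. The expected number is the sum over j = d to M − 1 of that probability times (M − j).

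- N = 3, d = 2, M = 2: the second DLT can fall only on the last subject, so the result is 0.
- N = 6, d = 3, M = 5: 2p³ + 3p³(1−p). At p = 0.30 this is 2×0.027 + 3×0.027×0.7 = 0.111.
- N = 10, d = 4, M = 9, with q = 1 − p: p⁴[5 + 4·4q + 3·10q² + 2·20q³ + 35q⁴]. At p = 0.30 this is 0.0081×(5 + 11.2 + 14.7 + 13.72 + 8.40) = 0.43.

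| True DLT rate | 30% | 40% | 50% | 60% |
|---|---|---|---|---|
| Groups of 3, infusions | 0 | 0 | 0 | 0 |
| Groups of 6, infusions | 0.11 | 0.24 | 0.44 | 0.69 |
| Groups of 10, infusions | 0.43 | 0.99 | 1.73 | 2.55 |
| Groups of 10, chance of closing early | 19% | 41% | 64% | 83% |

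At a true rate of 16%, a group of 10 closes early 2.7% of the time and saves 0.05 infusions.

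**4. Overlapping infusions.** With weekly infusions from day 14 and DLT onset uniform over days 0–28 (both assumed), groups of 10 give 0.28/0.67/1.25/1.93. If all later subjects are infused on one day, the figure is zero.

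**5. Whole trial, by simulation.** Assumptions: 30 subjects, one titration subject, start at 3×10^6, printed table on cumulative counts, sequential outcomes, no elimination rule, MTD by isotonic regression closest to 0.30. True rates are for 1/3/5/7×10^6.

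- 15/45/55/65% (3×10^6 already too toxic), groups of 10: infusions above target fall from 19.5 to 15.6, and DLTs from 10.4 to 9.2.
- 5/15/30/50%: with groups of 10, DLTs fall from 7.0 to 6.8 and correct MTD choice stays at 60%. With groups of 6, correct choice falls from 67% to 62%.
- 5/8/15/30%, groups of 6: correct choice falls from 72% to 67%.

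Over the scenarios with the MTD at 5 or 7×10^6, the loss is about 1–2 points in groups of 10 (nil to about 3, by scenario) and about 5 in groups of 6.

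**The case against.** The other side has four good points.

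- **The text only permits.** Groups may be as small as one, the table has a column for every number treated, and a site could read it after each subject. A reader might infer that the protocol orders infusions to continue past a de-escalate count. It does not, and deciding between cohorts is normal for BOIN. This stands, and the point claims a permission only.
- **Group sizes may be small.** The MTD example uses 3, 3, 15 and 9 subjects, all multiples of 3. It is an adjustable five-dose template, so it is weak evidence, but groups of 3 largely remove the problem. Ten at each of three levels plus the titration subject makes 31, above the maximum of 30. This limits the size of the finding but does not remove it, because Step 1 expressly allows 10.
- **Fully sequential outcomes are unlikely.** Ten subjects each observed for 28 days take about 280 days per level, which sits badly with a study period of December 2021 to December 2024. The sequential figures are therefore upper values.
- **Stopping at every table column would harm the trial.** One might read each column as a stopping rule. Counted that way, groups of 10 give 3.4 to 6.4 infusions past the row. But at a true 30% rate, 52% of groups would be held and 52% of those holds would not have ended in de-escalation at 10. Correct MTD choice under 5/15/30/50% would fall from 60% to 40%. That reading is not adopted.

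A contradiction might also be inferred because Step 2 divides by "the total number of subjects enrolled at the current dose level" while the table is headed "The number of patients treated at the current dose". With replacement of early leavers the two can agree. Using one term is optional tidying.

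**Conclusion.** The point holds in a limited form. As written, subjects may be infused at a level after de-escalation at the planned group size is already certain, and no other provision supplies a count-based stop. The exposure runs from none (first groups of 3 with a DLT-free first subject) to 2.5 infusions per group (groups of 10, sequential outcomes, 60% true DLT rate). At the 30% target it is at most about 0.4. These figures rest on assumed DLT rates, group sizes and timing. On a return to a level, cumulative counts apply and the per-group figures no longer hold exactly.

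A DLT in subject 1 by day 14 already keeps the gate shut, so the document does not support a claim that the group is unprotected from the start. Nor can group sizes at the higher doses be called missing while Figure 1 is unseen. This is a cheap improvement to the dosing rule.

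**What to change.** Add after the stagger rule:

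> *If the DLT count at a level already meets the printed de-escalate number for the planned group size, no further subject is lymphodepleted or infused at that level, and de-escalation follows at once.*

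It helps to state that this step down is exempt from the between-group observation gate, while subjects already infused complete their 28 days. Prompt de-escalation also matters for anyone already lymphodepleted: "If the infusion of cells is delayed for more than 5 days after lymphodepletion for any reason", infusion is barred or must be put off.

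The cost is one sentence and somewhat fewer data at closed levels, with the loss of MTD accuracy given above: about 1–2 points in groups of 10 and about 5 in groups of 6. Giving the planned group size for each BOIN level, if Figure 1 does not, and using one term for the denominator of the DLT rate are optional clarifications.
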